722 mass. In evaluating the relationship between altered EE by cool exposure/fasting and *ad libitum* food
723 intake, the concomitant RQ will also be included as further covariate in the multivariate model. Lastly,
724 sensitivity analyses accounting for the SPA inside the metabolic chamber will be done. Although we
725 anticipate that the wash-out period will remove any carry-over effect, potential order effects arising
726 from the cross-over design of the study will be assessed by including a dichotomous variable for the
727 sequence effect of interventions (e.g., 0 = “cold exposure & subsequent *ad libitum* food intake”; 1 =
728 cold & concomitant *ad libitum* food intake) in the multivariate models assessing the association
729 between change in EE and change in energy intake. Student t-tests will be also calculated to
730 determine if the change in EE or the change in energy intake differ between these two groups. If no
731 difference exists in the outcome variables between these 2 groups and the dichotomous variable is
732 not significant in the multivariate model, we will determine that no evidence for an order effect exists
733 and leave the dichotomous variable out of the final multivariate model. If there will be evidence of an
734 order effect, we will include the dichotomous variable in the multivariate model to ‘adjust’ for the
735 order effect.

736 To follow-up the regression analyses and assess potential causality linking EE to energy intake,
737 mediation analysis based on hierarchical multiple regression models as outlined in [66] will be used to
738 evaluate whether the effect of increased EE on energy intake is exerted through the influence of
739 mediators, including hormonal changes, RQ appetite sensations, behavioral and neurocognitive
740 scores. The Sobel test [67] will be used to test the significance of the mediation effect.

741 For all hormonal measures, the change in concentrations induced by the interventions will be
742 compared to the baseline fasting concentrations drawn prior to the energy balanced 24-h EE
743 assessment using paired t-tests for normally distributed data or the Wilcoxon nonparametric test for
744 skewed data. A sample size of 68 subjects will provide greater than 80% power with an alpha of 0.05
745 to detect a minimum mean expected decrease in fasting leptin, as a representative hormone, of
746 -1.8 ± 6.0 ng/mL as observed in prior studies measuring leptin concentrations during 24-h fasting [1].

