747 This sample size provides a similar power to detect a correlation of -0.30 at an alpha of 0.05 between
748 the decrease in any of the hormones and cold induced thermogenesis or the expected increase in
749 energy intake. Hormonal changes will be evaluated as possible contributors to the altered 24-h EE
750 and subsequent energy intake first in correlation analyses stratified by type of intervention (i.e., cold
751 exposure and 24-h fasting) and then using similar mixed models as described above. Additionally,
752 behavioral and cognitive test scores will be evaluated as possible predictors of the EE-energy intake
753 link, again using correlations and mixed models. The minimum expected correlation detectable in 68
754 subjects for any of the scores with changes in energy intake will equal 0.30, as reported above.
755 Differences in core body temperature and skin temperatures from measures during energy balance
756 will be calculated for fasting and cold exposure. The significance of these changes will be assessed
757 using one-sample t-tests. The association between these changes and percent body fat as well as EE
758 responses will be assessed using correlation coefficients as above, and again, the minimum detectable
759 correlation with 68 subjects equals 0.30. Significant associations will be evaluated further with mixed
760 models to account for repeated measures, sex, race and age and other potential confounders.
761 Associations between EE responses to each intervention and absolute weight change at each
762 follow-up visit will be quantified by regression models accounting for age, sex, race, and baseline

763 weight. All longitudinal analyses for future weight change will be confirmed using percent change in
764 weight as the dependent variable instead of absolute weight change. Similar models will be calculated
765 for the absolute changes in fat mass and fat free mass including baseline measures as covariates. In
766 case of significant associations between the EE responses to different intervention and weight
767 change, full regression models will be calculated to determine independence of the identified
768 predictors. Mixed model analysis will be used to evaluate the predictive effect of baseline EE
769 measures in relation to the body weight trajectory including all the follow-up visits and accounting for
770 repeated measures. The Compound Symmetry (CR) and the AR(1) covariance structures will be

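### The power stated for the secondary analyses with 68 subjects is too high: about 0.68 for the leptin change and 0.71 for a correlation of 0.30, where Table 2 itself asks for 84

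*Combined protocol and SAP*

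**What the plan says.** Four statements in the Data Analysis section concern what 68 subjects can detect in the secondary analyses.

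- **Hormone change.** "A sample size of 68 subjects will provide greater than 80% power with an alpha of 0.05" for a decrease in fasting leptin of -1.8 ± 6.0 "ng/mL as observed in prior studies measuring leptin concentrations during 24-h fasting". Leptin stands in for the hormones generally. The planned comparison is of change from baseline, "assessment using paired t-tests for normally distributed data or the Wilcoxon nonparametric test for" skewed data.
- **Hormone correlations.** "This sample size provides a similar power to detect a correlation of -0.30 at an alpha of 0.05 between" the fall in a hormone and either cold-induced thermogenesis or the rise in energy intake. The comparison refers back to the power of more than 80% just stated.
- **Behavioural and cognitive scores.** "The minimum expected correlation detectable in 68" subjects, for correlation with change in energy intake, is put at 0.30.
- **Core and skin temperatures.** The minimum detectable "correlation with 68 subjects equals 0.30".

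Table 2 in the Sample Size Calculation section gives the numbers needed for power of at least 0.8, with alpha labelled two-sided. For r = 0.30 at alpha = 0.05 it lists n = 84.

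On sidedness, the end of the Data Analysis section makes the primary tests two-sided at 0.01. It sets 0.05 per comparison for the secondary outcomes without saying one-sided or two-sided.

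**The concern.** For the same correlation, alpha and power target, Table 2 asks for 84 subjects while the Data Analysis section treats 68 as enough. The leptin sentence has the same problem in another form: a change of 1.8 against an SD of 6.0 is a standardised effect of 0.30, too small for 68 pairs to detect with 80% power at two-sided 0.05.

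These are the only power statements given for the hormone, behavioural and cognitive, and temperature aims. If they are too optimistic, a null result in any of these families will look like firmer evidence of no effect than the design can give.

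**Working it through.** **Inputs.** n = 68, alpha = 0.05, mean leptin change 1.8 and SD 6.0 ng/mL, |r| = 0.30 (Data Analysis); two-sided alpha and n = 84 for r = 0.30 (Table 2); printed powers for n = 68 (Table 3).

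**Step 1: reproduce the protocol's own correlation figures.** Take the critical correlation as r_c = t_c / √(t_c² + n − 2), with t_c the two-sided critical t on n − 2 df. Then

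power = Φ{ [atanh(r) + r/(2(n − 1)) − atanh(r_c)] × √(n − 3) }.

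| r = 0.30, n = 68 | Computed | Table 3 |
|---|---|---|
| alpha 0.01 | 0.470 | 0.470 |
| alpha 0.005 | 0.378 | 0.378 |

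Across all cells this two-sided formula agrees with Table 3 to within 0.002 and with Table 2 to within one subject (85 against the printed 84 for r = 0.30 at alpha 0.05). It is in effect the method the authors used.

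**Step 2: apply it to the secondary claim.** With n = 68, r = 0.30 and two-sided alpha 0.05:

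- t_c = 1.997 on 66 df, so r_c = 0.2387 and atanh(r_c) = 0.2434.
- atanh(0.30) + 0.30/134 = 0.3118.
- (0.3118 − 0.2434) × √65 = 0.55, and Φ(0.55) = **0.71**.

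The plain Fisher z approximation gives 0.704, and a simulation of 200,000 samples gives 0.710. The smallest correlation with 80% power at n = 68 is about **0.33** (0.332 before rounding; 0.330 itself gives 0.794).

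**Step 3: leptin, paired t-test.** Standardised effect d = 1.8/6.0 = 0.30. The noncentrality is d√n = 0.30 × √68 = 2.474, and the two-sided critical t on 67 df is 1.996. The noncentral t distribution gives:

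- power at n = 68: **0.684** (normal approximation 0.696);
- n for 80% power: **90** (0.804; n = 89 gives 0.799);
- smallest d with 80% power at n = 68: 0.345, that is 0.345 × 6.0 = **2.07 ng/mL**.

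If the data are skewed and the Wilcoxon test is used, its efficiency of 3/π under normality, taken as a rough guide, brings the power to about 0.66.

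**Step 4: one-sided alpha 0.05, for comparison.**

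| | Stated | Two-sided | One-sided |
|---|---|---|---|
| Leptin change | above 0.80 | 0.684 | 0.789 |
| r = 0.30 | similar to the leptin figure | 0.709 | 0.808 |

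**Step 5: the meaning of 6.0.** If 6.0 were the SD of leptin at each time point, the SD of the change would be 6.0 × √(2(1 − ρ)), where ρ is the within-subject correlation. The protocol gives no ρ. Two-sided power would then be 0.41 at ρ = 0, 0.68 at 0.5, 0.78 at 0.6 and 0.88 at 0.7, passing 0.80 a little above ρ = 0.62.

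**The case against.** The strongest reply is that the secondary tests may have been meant as one-sided. The protocol declares two-sided testing for the primary outcomes and in the footnote to Table 2, which concerns the primary association; for secondary outcomes it gives only 0.05. Each hormone has its own predicted direction in the Secondary Hypotheses, and the power text refers to a decrease and to a negative correlation. One-sided alpha 0.05 gives 0.81 for r = 0.30, so the correlation statements may well have come from a one-sided calculation. That is a plausible origin of the figures, but it does not rescue them. No one-sided test is declared anywhere, the leptin figure would still be 0.79 and not above 0.80, and no single direction is stated for the correlations with behavioural scores.

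Second, the leptin result depends on 6.0 being the SD of the within-subject change. That is the natural reading of a mean decrease followed by ±, given a paired test. On the other reading the claim holds only if the within-subject correlation exceeds about 0.62, a figure the protocol does not supply. The conflict over r = 0.30 does not depend on this.

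Third, the sample size was set by the primary association, not by these sentences, and the interim rule may raise it to 124. At 124 the two-sided power is about 0.91 for leptin and 0.93 for r = 0.30. This limits the practical consequence if the increase happens, but the statements at issue are explicitly about 68.

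**Conclusion.** The concern holds. With 68 subjects and two-sided alpha 0.05, power is 0.71 for a correlation of 0.30 and 0.68 for the stated leptin change, about 9 and 12 percentage points below 80%. The chance of missing an effect of the stated size is 29% and 32% respectively. The correlation statements contradict Table 2 directly (68 against 84 subjects), and 0.30 is not the minimum detectable correlation at 80% power; about 0.33 is.

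This rests on two-sided testing of the secondary outcomes and, for leptin only, on 6.0 being the SD of the change. It does not affect the primary sample-size calculation. It should be corrected because it is the stated basis for reading the secondary results.

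**What to change.** In the Data Analysis section, state that the secondary tests are two-sided at 0.05 and replace the power sentences with wording such as:

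> At two-sided alpha 0.05, 68 subjects give 80% power to detect a correlation of about 0.33 in absolute value, or a mean leptin change of about 2.1 ng/mL if the SD of the change is 6.0 ng/mL. Power is 0.71 for a correlation of 0.30 and 0.68 for a leptin change of 1.8 ng/mL.

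Replace 0.30 with 0.33 in the two later statements of the minimum detectable correlation (behavioural and cognitive scores; temperatures), and say explicitly that 6.0 is the SD of the change. If one-sided tests were intended, declare and justify them for each hypothesis; the leptin statement would still have to be lowered to 0.79.

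The cost is wording only: slightly less favourable figures, with no change to enrolment, procedures or tests.

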1 INTRODUCTION

2 Energy Expenditure and Energy Intake Link

3 The fundamental principle of energy balance states that energy intake and energy expenditure
4 (EE) are the counterbalancing factors that determine body weight change. Both components are likely
5 influenced by environmental and genetic factors; however, while energy intake can vary largely from
6 day to day due to psychological and social influences, daily sedentary EE is largely determined by body
7 size and composition. An increased energy intake leads to a small increase (~10% on average) in EE
8 known as the diet-related energy expenditure [1]. In contrast, we have found in a previous study that
9 larger individuals have both a higher absolute EE due to a larger amount of fat-free mass and also, eat
10 a greater amount of food in an *ad libitum* setting both as total kilocalories and as a percentage of
11 weight maintaining energy needs [2]. As the 24-h EE measures done in this study were done during a
12 eucaloric diet (achieved energy balance within 20%), this correlation is likely because body energy
13 requirements modulate a physiological signal for hunger that results in increased food intake [2, 3]. Of
14 note, during the *ad libitum* portion of the study, participants ate more than their weight maintaining
15 energy requirements on average, suggesting that relatively higher energy demands may lead some
16 people to overeat to a greater degree in a food rich environment. A previous study by Caudwell *et al.*
17 also found a direct correlation between resting EE (RMR) and food intake as well as hunger sensations
18 measured during a 3-month trial [3]. Interestingly, after accounting for fat free mass, fat mass is
19 negatively associated with subsequent food intake [2]. The effects of EE on food intake may act, in
20 part, through central pathways that modulate appetite as fat free mass, the primary determinant of
21 resting EE, has been associated with food intake [4] and reduced gray matter volume in regions
22 implicated in energy homeostasis [5].

23 From an evolutionary viewpoint, a link between energy expenditure, i.e. energy needs, and
24 food intake would ensure that an organism would experience a physiologic drive to find enough food
25 to maintain both life and reproduction. Although some studies have found an inverse association
26 between lower-than-predicted EE and future body weight change [6, 7], others have found that a

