771 evaluated and compared by the BIC statistic to identify the best model for weight data over time.
772 Changes in EE after 24-h of fasting and its association with changes in body weight at 6 months and 1
773 year will be combined with data from prior studies (using the exact same methodology) to increase
774 the statistical power of the weight change analysis (currently we have >60 subjects with complete
775 data available at baseline).

776 Statistical analysis will be performed using SAS with E-guide (SAS Institute, Cary, NC). All tests
777 of primary outcome measures will have a 2-sided Type 1 error of $p=0.01$. For the secondary outcome
778 analyses, we will control for Type 1 error at the level of the comparison with $p=0.05$ as each
779 hypothesis is substantively important and stated *a priori*.

780 **Informed Consent Process**

781 Written informed consent will be obtained from the participant prior to any screening visits,
782 study procedures or treatments. The person obtaining consent will explain the study in language
783 understandable to the subject. Sufficient time and opportunity will be given for discussion of the
784 research as well as to answer any questions they may have, taking care to minimize or eliminate the
785 perception of coercion or undue influence. The participant and the investigator will sign the current
786 IRB-approved informed consent document. A copy of the consent will be given to the subject for
787 future reference. The signed documents will be sent to the Medical Records Department for
788 placement in the subject's permanent record.

789 Participants will have the opportunity to carefully review the written consent form, either as a
790 physical or electronic document, and ask questions prior to signing. Participants will be informed that
791 participation is voluntary and that they may withdraw from the study at any time, without prejudice.

792 The consenting process may be performed using the NIH iMedConsent platform (which is 21
793 CFR Part 11 compliant). If the iMedConsent platform is used, then the participant and consenting
794 investigator will review and sign the current IRB-approved electronic informed consent document
795 using a hand signature (e.g., signing using a finger, stylus, or mouse). Electronic signatures (i.e., the
796 “signature” and a timestamp are digitally generated) will not be used. If a paper copy of the IRB-

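### Temperature-change associations are adjusted for sex, race and age only if the crude correlation is significant, so one masked by sex could be reported as null (minor, secondary analyses)

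*Combined protocol and SAP*

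**What the plan says.** All of this is in the Data Analysis section of the combined protocol and SAP.

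- **First step.** Differences in core and skin temperature from the energy-balance day are calculated for cold exposure and for fasting. "The association between these changes and percent body fat as well as EE" "responses will be assessed using correlation coefficients as above, and again, the minimum detectable" correlation is then stated: "correlation with 68 subjects equals 0.30". The coefficients meant are the Pearson or Spearman correlations defined earlier in the section, which carry no covariates.
- **Second step.** "Significant associations will be evaluated further with mixed" "models to account for repeated measures, sex, race and age and other potential confounders". Adjustment is thus conditional on the crude result.
- **Level.** For secondary outcomes, "analyses, we will control for Type 1 error at the level of the comparison with $p=0.05$ as each" hypothesis is regarded as important and specified in advance. Sidedness is not stated for these outcomes.

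Three neighbouring analyses carry no such condition. Hormone changes go through correlations and then mixed models. Behavioural and cognitive scores go through correlations and mixed models. The EE response itself has a mixed model with age, sex, race, percent body fat, aerobic capacity and intervention type as fixed effects. Temperature is not a term in that last model, and no other part of the plan adjusts a temperature association.

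**The concern.** A crude correlation mixes the within-sex relationship with the difference between the sexes. If women and men differ in percent body fat, and also differ in temperature change in the direction opposite to the within-sex slope, the two components cancel. The crude correlation then shrinks towards zero. Under the rule as written the analysis stops there, although sex is recorded for every participant and the model that would separate the components is already described.

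What is at stake is part of Secondary Aim 3 and Secondary Hypothesis 3: whether skin and core temperature changes relate to adiposity and to the EE response. A null could be reported because of the order of the steps, with no adjusted estimate for a reader to examine.

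**Working it through.** **1. The plan's own figure.** Inputs: n=68, r=0.30, alpha 0.05. The power is described only by reference to the leptin calculation just before it, which claims more than 80%: "This sample size provides a similar power to detect a correlation of -0.30 at an alpha of 0.05 between" hormone decreases and cold-induced thermogenesis or intake. By Fisher's z, atanh(0.30) × √65 = 0.3095 × 8.062 = 2.495.

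- One-sided: Φ(2.495 − 1.645) = 0.802. This reproduces the claim.
- Two-sided: Φ(2.495 − 1.960) = 0.704 (0.711 by simulating the sampling distribution of r). This does not.

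Table 2, which is two-sided, lists n=84 for r=0.30 at 0.05; the same simulation gives 0.801 there. The mismatch is a side issue. I take the screening test as two-sided, as an assumption consistent with Table 2.

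**2. Threshold to reach adjustment.** With 66 degrees of freedom the critical t is 1.997, so |r| must exceed 1.997 / √(66 + 1.997²) = 0.239.

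**3. How sex moves the crude correlation.** Let ρ be the within-sex correlation, dx the sex difference in percent body fat and dy the sex difference in temperature change, both in within-sex SDs. With equal numbers of women and men:

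crude r = (ρ + 0.25·dx·dy) / √[(1 + 0.25·dx²)(1 + 0.25·dy²)]

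The documents give none of these values. Assumed: ρ = −0.40, dx = 1.25, 34 per sex. Example, dy = +0.5: (−0.40 + 0.156) / √(1.391 × 1.0625) = −0.244 / 1.216 = −0.20, inside the threshold.

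If sex acted only through body fat, dy would be ρ·dx = −0.5. The direct sex effect implied by any dy is therefore dy + 0.5.

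**4. Simulation.** 20,000 trials per setting; crude Pearson test against a sex-adjusted partial correlation test, both two-sided 0.05. Blocked means the adjusted test is significant but the crude test is not.

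| dy (SD) | Direct sex effect (SD) | Crude r by formula | Crude significant | Adjusted significant | Blocked |
|---|---|---|---|---|---|
| 0 | +0.5 | −0.34 | 82% | 93% | 12% |
| +0.3 | +0.8 | −0.26 | 56% | 93% | 37% |
| +0.5 | +1.0 | −0.20 | 36% | 93% | 57% |
| +0.8 | +1.3 | −0.12 | 14% | 93% | 79% |
| −0.5 (through body fat only) | 0 | −0.46 | 98% | 93% | 0.3% |
| −0.3 | +0.2 | −0.41 | 95% | 93% | under 2% |
| −0.8 | −0.3 | −0.51 | 99.6% | 93% | 0.0% |
| no sex difference in either variable | 0 | −0.40 | 93% | 93% | 0.3% |

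**5. Wider ranges.** For within-sex correlations of size 0.3 to 0.5, body-fat differences of 1.0 to 2.0 SD and offsetting temperature differences of 0.4 to 1.2 SD, the blocked share runs from 0.15 to 0.96. With no net sex difference in temperature change it runs from 0.02 to 0.32.

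**6. Limits of the calculation.** It represents temperature change with percent body fat. The mechanism is the same for temperature change with EE response, but the 1.25 SD input does not apply there and that pair is not quantified. Only sex is adjusted; race, age and repeated measures are left out.

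**The case against.** The strongest reply is that the loss is assumed, not shown. The documents contain no sex-specific data on temperature change or EE response; the sex coefficients in Table 1 concern food intake. Without an opposing effect the condition costs almost nothing. With a reinforcing sex difference, sending significant crude results on to an adjusted model is useful protection against confounded positives. The analyses are secondary, the study calls itself proof-of-concept, and the sentence does not forbid further models. All of this stands and keeps the point minor. It does not remove it: the direction is unknown in advance, and a later unplanned model is weaker evidence than a planned one.

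Three stronger readings are tempting and are not supported.

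- **That screening on crude significance loses power in itself.** The dy = 0 row looks like evidence, but it contains a direct opposing effect of 0.5 SD. Without one, the blocked share is 0.3%.
- **That all of Secondary Hypothesis 3 is screened.** Its first part, adiposity and the EE response, is covered by the mixed model for EE response, which is fitted whatever the crude result (although BIC chooses the number of predictors).
- **That the Introduction already documents such masking.** The remark beginning "Interestingly, after accounting for fat free mass, fat mass is" concerns food intake and adjustment for fat-free mass, so exposure, outcome and adjuster all differ. The crude association is not given there either.

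**Conclusion.** The point holds for two sets of associations only: temperature change with percent body fat, and temperature change with EE response. For these, the plan can report a null that its own adjusted model would contradict. The loss ranges from negligible to most trials, and where it falls depends entirely on an opposing sex effect that the documents neither establish nor rule out. The percentages rest on the assumed within-sex correlation, the assumed sex differences, an equal split by sex and a two-sided 0.05 test. It is a cheap improvement to a secondary analysis. The primary EE-to-intake analysis is unaffected.

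**What to change.** In Data Analysis, replace the sentence that makes the mixed models conditional on significance. Suggested wording: the mixed model adjusted for sex, age and race will be fitted for every pre-listed association of core or skin temperature change with percent body fat and with EE response, whatever the p-value of the crude correlation; its estimate and confidence interval will be reported alongside the crude correlation, which is descriptive.

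This brings the temperature analyses into line with the hormone and behavioural ones, which already proceed to mixed models unconditionally. The cost is one sentence, a list of the associations, a few degrees of freedom per model and more output. No new data are needed.
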